10.6. Safety Evaluations

Investigators are responsible for monitoring the safety of patients who have entered this study and for alerting Lilly or its designee to any event that seems unusual, even if this event may be considered an unanticipated benefit to the patient.

The investigator is responsible for the appropriate medical care of patients during the study. Planned safety assessments and measures are detailed in Section 10.6.3, but additional assessments and safety tests may be performed at the investigator's discretion.

The investigator remains responsible for following, through an appropriate health care option, AEs that are serious, considered related to study treatment or the study, or that caused the patient to discontinue before completing the study. The patient should be followed until the event is resolved or explained. Frequency of follow-up evaluation is left to the discretion of the investigator.

In addition to records of observations made at specific times, unexpected signs and symptoms and concomitant medications will be recorded in the clinical trial records throughout the study.

Safety monitoring will include MRIs, AEs, ECGs, vital signs (blood pressure, pulse rate, and temperature), physical and neurological examinations, C-SSRS, and safety laboratory tests (including LP clinical laboratory tests).

For Part A, MRI safety monitoring will consist of a baseline MRI, a Week 4 postdosing MRI, and a Week 12 postdosing MRI, with sequences appropriate for detecting vasogenic edema and microhemorrhage. MRIs at baseline, 24 weeks, 48 weeks, and 72 weeks are for volumetric assessment. Additional MRI measures may be obtained at these ARIA-related and/or MRI time points.

For Parts B and C, MRI safety monitoring will consist of a baseline MRI, a Week 4 postdosing MRI, and a Week 12 postdosing MRI, as well as MRIs every 12 weeks until 48 weeks (Part B) and 12 weeks (Part C) after the last dose. MRIs at baseline, 24 weeks, 48 weeks, and 72 weeks are for volumetric assessment. Additional MRI measures may be obtained at these ARIA-related and/or MRI time points.

Determination of the number of microhemorrhages will be required to be assessed on a 1.5T or 3T MRI, as the greatest understanding of the number of microhemorrhages and their relationship to disease are associated with these magnet strengths.

Dose-escalation methods are presented in Section 9.4 and stopping criteria are presented in Section 8.2. Safety evaluations of Cohorts 1 and 2 will be performed after a minimum of 5 patients (4 patients on LY3002813 and 1 patient on placebo) have concluded the 4-week period and completed all required testing. Any remaining patients not reviewed for the Cohort 1 and Cohort 2 evaluations will undergo a 4-week safety evaluation when all have completed 4-week safety assessments.

Regular safety evaluations across all cohorts will be performed at 3-monthly intervals. All new data as listed above will be included, in addition to the local CSF laboratory tests. Each geography (which may mean separate meetings in the United States and in Japan) will meet as described above to determine whether stopping rules are met.

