In the SAD portion of Study AACC, it was observed that LY3002813 had a significantly shorter half-life than the approximately 24-day half-life predicted based on data from nonclinical studies (a prediction that was consistent with the expected half-life of an immunoglobulin G1 antibody [Lobo et al. 2004]). After single-dose administration from 0.1 mg/kg to 3.0 mg/kg, the mean terminal elimination half-life was approximately 4 days, increasing to approximately 10 days (243 hours) at the 10-mg/kg dose level. The PK of a single dose of 1.0 mg/kg IV LY3002813 in young, healthy subjects was indistinguishable from the PK in AD patients at the same dose level. In the MAD phase, most patients at dose levels \leq 3 mg/kg had serum LY3002813 concentrations below the limits of detection 28 days after dosing; patients receiving 10 mg/kg did have sustained quantifiable concentrations 28 days after dosing.

Greater than 90% of the patients with AD had treatment-emergent antidrug antibodies (ADAs) 3 months after the first dose at all dose groups; titers tended to increase by the end of the MAD phase and persist 3 months after the last dose. Dosing was stopped in the MAD phase of Study AACC because of high prevalence of ADAs and unexpected rapid elimination of the study drug.

Sixteen adverse events (AEs) of mild or moderate infusion related reactions were reported in 6 of 51 patients dosed with LY3002813. Infusion reactions occurred in 1 patient in the 0.3-mg/kg cohort, 2 patients in the 1.0-mg/kg cohort, and 3 patients in the 3.0-mg/kg cohort. The infusion reactions developed in 1 of the 6 patients after the first MAD dose and in 5 of the 6 patients after the second MAD dose. One patient discontinued because of dyspnea due to an infusion reaction (mild severity). All patients with infusion reactions had high peak titers of ADAs. Three patients were rechallenged with premedication (acetaminophen, antihistamine, and/or hydrocortisone) and had milder reactions on rechallenge. Infusion reactions began during the infusion or within 30 minutes of completing the infusion and lasted between 1 minute and 8 hours. Symptoms included chills/shivering (3 patients); flushing (2 patients); hypotension (asymptomatic, 1 patient); dyspnea (1 patient); myalgia (1 patient); rash (1 patient); and fever (1 patient).

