7.1. Summary of Study Design

[figure not shown]
This is a Phase 1b, patient- and investigator-blind, randomized within cohort, placebo-controlled, parallel-group, single- and multiple-dose study in patients with MCI due to AD or mild to moderate AD to assess the safety, tolerability, PK, and PD of single and multiple IV doses of LY3002813.

This study (Study AACD) will enroll patients with MCI due to AD, mild AD, or moderate AD with amyloid deposition confirmed by florbetapir PET imaging using National Institute on Aging-Alzheimer's Association (NIAAA) work group consensus guidelines (Albert et al. 2011; McKhann et al. 2011). This study will be conducted at sites in multiple countries, including the United States and Japan. Up to 150 patients may be enrolled so that approximately 72 patients (7 dosing cohorts of 8 to 12 patients) complete the study.

[figure not shown]
The study will be conducted in at least 7 cohorts ([Figure AACD.7.1](#)):

- Cohort 1: 10 mg/kg IV single dose
- Cohort 2: 20 mg/kg IV single dose
- Cohort 3: 40 mg/kg IV single dose
- Cohort 4: 10 mg/kg IV every 2 weeks (Q2W) for 24 weeks
- Cohort 5: 20 mg/kg IV Q2W for 24 weeks
- Cohort 6: 10 mg/kg IV Q4W for up to 72 weeks
- Cohort 7: 20 mg/kg IV Q4W for up to 72 weeks

[figure not shown]
Part A: Single dose; 72-week follow-up (Cohorts 1 & 2), 24-week follow-up (Cohort 3)

Part B: 24-weeks, Q2W multiple dose treatment; 48-week follow-up

Part C: Chronic dose, 72-week, Q4W multiple dose treatment; 12-week follow-up

Abbreviations: f/u = follow up; IV = intravenous; MRI = magnetic resonance imaging; PET = positron emission tomography; Q2W = every 2 weeks; Q4W = every 4 weeks; x = times.

Assessments: A = amyloid PET; I = immunogenicity; M = MRI; T = tau PET; C = cognition; F = cerebrospinal fluid.

D = dosing; S = 4 week safety review of Cohort 2.

Follow-up assessments (immunogenicity, I; MRI, M) 12 weeks after last dose for Cohorts 6 and 7.

Note: vertical lines indicate 4-week intervals. Additional immunogenicity assessments will be performed every 12 weeks up to 48 weeks after the last dose of LY3002813 if the antibody titer has not returned to baseline.

Figure AACD.7.1. Study design.

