7.1.5. Part C: Chronic, 72-Week Q4W Multiple Dose Cohorts (Cohorts 6 and 7)

Safety, PK, and PD will be assessed in Cohorts 6 and 7 during and after multiple doses of LY3002813 or placebo have been administered Q4W for up to 72 weeks, or when the LY3002813-induced reduction in amyloid measured by florbetapir reaches the maximum reduction (defined as SUVr <1.1 for 2 consecutive scans) (Joshi et al. 2015). The planned doses are 10 and 20 mg/kg IV with 12 patients (9 LY3002813; 3 placebo) planned to be enrolled in each cohort. Cohort 6 (10 mg/kg IV Q4W) and Cohort 7 (20 mg/kg IV Q4W) may proceed, in parallel with Cohorts 4 and 5, respectively. In addition, Cohort 7 will only be initiated after confirmation that at least 2 patients have received at least 2 doses each of LY3002813 safely in Cohort 6. The maximum dose of 20 mg/kg will not be exceeded. If a patient is deemed to be amyloid negative by florbetapir PET before completion of 18 months' dosing (SUVr <1.1 for 2 consecutive scans), the patient will receive placebo infusion for all subsequent visits and continue the Part C visit schedule, including assessment of sustained amyloid reduction at the scheduled PET scan assessments. Safety, PK, and PD will be assessed for all patients at regular intervals for approximately 12 weeks after completion of 72 weeks of dosing with LY3002813 ([Attachment 1](#)).

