Multiple doses of 10 mg/kg IV were safe and tolerated in Study AACC. Although infusion reactions were observed in 6 out of 51 patients dosed with LY3002813, there were no infusion reactions in the 10 mg/kg dose cohort, despite the presence of ADAs. Clinical dosing of single dose of 20 mg/kg or multiple dosing of 10 mg/kg in Study AACD will only be initiated after safety review of the single 10-mg/kg dose of LY3002813.

MRI safety monitoring will occur 4 weeks after the first dose, every 12 weeks from the first dose, and up to 12 weeks after the last dose, with acquisition of sequences appropriate for

detecting vasogenic edema and microhemorrhage. These MRIs and MRIs at additional time points (ie, at 24 weeks, 48 weeks, and 72 weeks) will also provide volumetric and other imaging biomarker assessments. Microhemorrhages are believed to indicate a higher risk for macrohemorrhage as well as for the presence of significant amyloid angiopathy, and there appears to be a risk of microhemorrhage with antiamyloid treatment in preclinical models and in humans (eg, bapineuzumab, gantenerumab, aducanumab [Black et al. 2010]) as well. Although there was no evidence of ARIA-E by MRI at up to 10 mg/kg LY3002813 in Study AACC, this study will continue to monitor ARIA-E (and ARIA-H). The screening MRI scan will be used to exclude patients with >4 microhemorrhages. The 12-week interval between MRI scans is considered appropriate given the lack of ARIA-E observed up to 10 mg/kg LY3002813 in Study AACC.

8. Study Population

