9.5.1.3. Recognition and Management of Cerebral Vasogenic Edema

Antiamyloid therapies that have some similarities to LY3002813 have been associated with cerebral vasogenic edema (ARIA-E) with and without microhemorrhage (ARIA-H). Most of these cases are asymptomatic and have been detected by routine brain MRI. When symptoms are present in association with these imaging abnormalities, they have been reported to include headache, gait instability, dizziness, tremor, worsening cognitive function, alteration of consciousness, seizures, unsteadiness, and/or vomiting. In most cases (even when symptomatic), these imaging abnormalities have not required treatment other than discontinuation of the investigational compound, and imaging abnormalities have resolved. Infrequently, high-dose steroid therapy has been administered in the presence of prominent symptoms.

If the symptoms above are reported and vasogenic edema is suspected, then the abnormality is best detected by FLAIR sequences on MRI and microhemorrhages are best detected with the T₂*-weighted gradient-echo sequence on MRI. An unscheduled MRI with these sequences should be obtained upon suspicion of cerebral vasogenic edema. It is recommended that MRI be repeated with these sequences every 2 to 4 weeks until resolution of vasogenic edema is documented. For asymptomatic or mild symptoms, the patient can be observed; for moderate symptoms, the use of oral or IV steroids can be considered. In the case of severe symptoms, it is recommended that the patient be hospitalized for close observation; the use of IV steroids, such as high-dose dexamethasone or a similar agent, should be considered. Such medications, if used, should be entered into the concomitant medications CRF. If asymptomatic or symptomatic vasogenic edema occurs, the patient must not receive further dosing and should undergo discontinuation procedures.

Patients who present with new clinically asymptomatic microhemorrhages should have a repeat MRI approximately every 4 weeks until stabilization.

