10.6.3.7. Magnetic Resonance Imaging

MRI scans will be obtained at time points indicated in the Study Schedule ([Attachment 1](#)).

MRI safety monitoring will consist of MRIs with sequences appropriate for detecting vasogenic edema and microhemorrhage (ARIA-E and ARIA-H). The number of microhemorrhages detected on the baseline MRI scan will serve as 1 factor in the exclusion criteria (that is, exclusion of patients with >4 microhemorrhages). Microhemorrhages might indicate a higher risk for macrohemorrhage, as well as the presence of significant amyloid angiopathy, and there appears to be a risk of microhemorrhage with some antiamyloid treatments in preclinical models and possibly in humans as well.

The determination of the number of microhemorrhages will be required to be assessed on a 1.5T or 3T MRI using a T₂*-weighted gradient-echo sequence. Additional FLAIR images will be performed to evaluate for the presence of vasogenic edema. All baseline and safety imaging will be analyzed by a central reader blinded to treatment.

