Visit No.:	V4 ^a	V5 ^b	V6	V7	V8	V9	V10	V11	V12	V13	V14	V15	V16	V17	V18	V19	V20	V21	V22	V23	V24	V25	
Day Relative to First Dose	-4	1	8	15	29	57	85	113	141	169	197	225	253	281	309	337	365	393	421	449	477	505	
Week		1	1	2	4	8	12	16	20	24	28	32	36	40	44	48	52	56	60	64	68	72	
Tolerance Interval for Visit (days)	±4*	0	±1	±1	±4	±4	±4	±4	±4	±4	±4	±4	±4	±4	±4	±4	±7	±7	±7	±7	±7	±7	
Laboratory Assessments (continued)																							
Clinical chemistry, electrolytes, hematology, urinalysis ^g		X			X	X	X	X	X	X	X	X	X	X	X	X	X	X	X	X	X	X	
Coagulation tests (at local laboratory, prior to LP) ^y	X										X												
Serum LY3002813 PK ^q		predose, end of infusion, 3, 24, 48, 72 hrs	X	X	X ^r	X ^r	X ^r	X ^r	predose, end of infusion 3, 24, 48, 72 hrs	predose, end of infusion 72 hrs	X ^r												
Plasma Aβ	X	72 hrs									X												
Serum for immunogenicity ^s	X		X	X	X		X				X			X			X		X		X		
Aliquoted plasma (EDTA) and serum for storage	X				X									X			X		X		X		
Stored serum for possible exploratory immune safety laboratory tests ^t	X						X				X			X								X	

Schedule of Activities, Protocol I5T-MC-AACD, Part C: Cohorts 6 and 7 (Chronic Dose), Visit 26 through Visit 27

Procedure	M18	FU	
Visit No.:	V26	V27	ED
Day Relative to First Dose	533	589	
Week	76	84	
Tolerance Interval for Visit (days)	±7	±7	
Entry and Administrative/Every Visit			
Body weight		X	X
Previous/concomitant medications	X	X	X
Preexisting conditions/AEs	X	X	X
Cognitive Assessments			
ADAS-Cog ₁₄			X
ADCS-MCI-ADL24			X
NTB			X
CDR			X
FCSRT-IR			X
MMSE			X
Safety Assessment			
Vitals	X	X	X
C-SSRS ^d /SHSF ^f	X	X	X
Physical/neurological examination	X	X	X
12-lead digital ECG ^e	X	X	X
Imaging			
MRI ^{h,i}			X
Florbetapir PET scan			X
18F-AV-1451 PET scan			X ^j
Laboratory Assessments			
LP ⁿ			X ^z
ABI tempus tube/blood RNA			X

Schedule of Activities, Protocol I5T-MC-AACD, Part C: Cohorts 6 and 7 (Chronic Dose), Visit 26 through Visit 27

Procedure	M18	FU	
Visit No.:	V26	V27	ED
Day Relative to Study Medication Start	533	589	
Week	76	84	
Tolerance Interval for Visit (days)	±7	±7	
Laboratory Assessments (continued)			
Clinical chemistry, electrolytes, hematology, urinalysis ^g	X	X	X
Coagulation tests (at local laboratory) ^y			X
Serum LY3002813 PK ^q	X	X	X
Plasma A β	X	X	X
Serum for immunogenicity ^s	X	X	X
Aliquoted plasma (EDTA) and serum for storage	X	X	X
Stored serum for possible exploratory immune safety laboratory tests ^t		X	X

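### Part C: the safety MRI that the text requires 12 weeks after the last dose (Week 84, V27) is not in the Study Schedule, so no scheduled MRI follows the final infusion

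*Protocol*

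**What the plan says.** The narrative text carries Part C safety MRI to 12 weeks after the last dose in several places.

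- Protocol Section 10.6 sets Weeks 4 and 12 for Parts B and C, "as well as MRIs every 12 weeks until 48 weeks (Part B) and 12 weeks (Part C) after the last dose".
- The legend of Figure AACD.7.1 (Section 7.1) lists "Follow-up assessments (immunogenicity, I; MRI, M) 12 weeks after last dose for Cohorts 6 and 7". The figure note in SAP Section 3.4 says the same.
- Section 7.2 describes MRI monitoring 4 weeks after the first dose, "every 12 weeks from the first dose, and up to 12 weeks after the last dose". Section 10.5.2 repeats this and puts the maximum number of post-baseline MRIs at 8.

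The operational instruction is in Section 10.6.3.7: "MRI scans will be obtained at time points indicated in the Study Schedule". In Attachment 1, the table headed "Schedule of Activities, Protocol I5T-MC-AACD, Part C: Cohorts 6 and 7 (Chronic Dose), Visit 26 through Visit 27" has three columns: V26, V27 and ED. Its MRI row has one mark, under ED. The preceding Part C table has its last MRI mark at V25, which is also the last dosing visit.

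**The concern.** Sites work from the Study Schedule, and Section 10.6.3.7 tells them to. A site that follows it will not book an MRI at V26 or V27 for a patient who completes Part C, although the text plans one at V27.

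At stake is asymptomatic ARIA arising after the final infusion. Symptomatic cases have a route: Section 9.5.1.3 calls for an unscheduled MRI when edema is suspected, and neurological examinations are scheduled at V26 and V27. But the same section says of similar antiamyloid therapies: "Most of these cases are asymptomatic and have been detected by routine brain MRI". Imaging on suspicion therefore does not replace the routine scan, and the repeat MRIs that Section 9.5.1.3 recommends until resolution cannot start for a case nobody has seen.

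Drug is still present in this window. Section 5.1 reports a half-life "increasing to approximately 10 days (243 hours) at the 10-mg/kg dose level". Section 5.2 makes a low incidence of ARIA-E and ARIA-H one of the conditions for further development, so missed cases bear on a stated decision. The additional immunogenicity and safety visits in Section 10.4.1 do not fill the gap, because they include no MRI.

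**Working it through.** **Dates.** Part C has 19 doses every 4 weeks (Synopsis).

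- Last dose: Day 1 + 18 × 28 = Day 505, which is V25, Week 72.
- Twelve weeks later: 505 + 84 = Day 589, which is V27, Week 84.

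**Number of scans.** Section 10.5.2 allows up to 8 post-baseline MRIs.

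- Part C by the rule in Section 10.6: Weeks 4, 12, 24, 36, 48, 60, 72, 84 = 8. This reproduces the stated maximum.
- Part B by the same rule (last dose Week 24, plus 48 weeks): Weeks 4, 12, 24, 36, 48, 60, 72 = 7. Among regular scheduled scans, only the Part C Week 84 scan brings the count to 8.
- Part C in Attachment 1: 7 marks up to V25, none at V26 or V27 = 7.

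Scheduled MRIs after the final infusion for a completer: 1 by the text, 0 by the schedule.

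**Reading the table.** In the V26/V27/ED table, body weight and stored serum are marked at V27 and ED, and concomitant medications and immunogenicity at all three. MRI, florbetapir PET and ADAS-Cog are marked at ED only. The row positions are consistent. In the earlier Part C table the MRI marks before V25 appear shifted by about one column. Only its last mark (V25) and the total of 7 are used here.

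**Who is affected.** Part C plans 9 active and 3 placebo patients in each of two cohorts.

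- Active: 2 × 9 = 18 at most. The 6 placebo patients are not at risk from drug, and early discontinuers have an ED MRI.
- For patients with SUVr below 1.1 on two consecutive scans, Section 7.1.5 says "the patient will receive placebo infusion for all subsequent visits and continue the Part C visit schedule". PET is at Weeks 12, 24, 36, 48 and 72, so the last scan that can trigger a switch during dosing is Week 48. Their V25 MRI then falls 72 − 48 = 24 weeks after the last active dose, or 20 weeks if one more active dose precedes the read. They are not affected.

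**Drug still present.** Five half-lives at 243 hours = 1215 hours = 50.6 days. With the 24-day half-life originally predicted (Section 5.1), it is 5 × 24 = 120 days, longer than the 84-day follow-up.

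**Chance that at least one case has no scheduled scan.** P = 1 − (1 − p)^n, where p is the probability per patient of asymptomatic ARIA in the 84 days. The documents give no value for p. The values below are assumptions.

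| p | n = 18 | n = 9 |
|---|---|---|
| 0.02 | 0.305 | 0.166 |
| 0.05 | 0.603 | 0.370 |
| 0.10 | 0.850 | 0.613 |

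**The case against.** The strongest objection is that the point rests on one blank cell in a table read from converted text. Aligned neighbouring rows rule out a shifted mark but not a dropped one, and MRI rows in other tables of Attachment 1 are visibly displaced. This stands as a reason to look at the PDF page. It is not a likely explanation: the single mark sits under ED with the PET and cognitive rows, and rows that should show V27 do so.

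Second, the scan is in the plan, so the blank is a clerical slip rather than a choice to omit it. That is probably right about intent. It does not help, because the protocol names the schedule as the source of MRI time points.

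Third, the assumed rates leave out Study AACC, in which no ARIA-E was seen up to 10 mg/kg (Section 7.2). It is fair to let p run down towards zero. But the 10 mg/kg group described in Section 5.2 had 6 patients, and zero events in 6 gives a one-sided 95% upper limit of 1 − 0.05^(1/6) = 0.39, so it excludes none of the values used. Also, 18 assumes that nobody discontinues or switches; the n = 9 column shows the effect of halving it.

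Fourth, some consequences are limited:

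- The SAP shift table would still hold up to seven scans after the first dose.
- V25 has a ±7-day window, so its MRI could fall a few days after the infusion, though that cannot stand in for a Week 84 scan.
- The 243-hour half-life comes from single 10 mg/kg doses, while Cohort 7 receives 20 mg/kg repeatedly.
- The patient has no further dosing decision, and asymptomatic cases may simply be observed.

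These points are correct. Even so, a late case would still count towards the cohort rule of two or more ARIA-E patients in Section 8.2.1.3, and towards the reported incidence.

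**Conclusion.** The concern holds. Current protocol text requires a Part C safety MRI at Week 84, and the schedule that sites are told to follow does not contain it. The count of 8 scans under the text rule, against 7 in the schedule, supports this reading.

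The gap is 84 days, for at most 18 patients on active drug, and it concerns asymptomatic ARIA only. The contradiction does not depend on any assumed ARIA rate; the probabilities in the table only illustrate its possible size. The conclusion assumes that the V27 MRI cell is also blank in the PDF. It should be corrected: this is a real gap in safety monitoring, but it is confined to follow-up, with symptomatic cases still covered.

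**What to change.** Add an MRI mark at V27 (Day 589) for Cohorts 6 and 7 in Attachment 1, to match Section 10.6 and the figure legend. State in SAP Section 4.2.7.2 that this scan enters the pre- and postdose ARIA shift table, so that the period after the last dose is represented.

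The cost is one cell in the schedule and one sentence in the SAP. V27 is an existing visit. The change means at most one MRI per Part C completer, up to 24 including placebo patients, and the text already plans those scans.
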